8.4 Data sources

Data used to collect variables will include any clinical document provided by patients or available in our hospital thank to the server of the Unit of Neurology. Only official clinical charts will be considered. Clinical outcomes will be defined as the age of loss of ambulation, the age of introduction of cardiological supporting drugs and the age of introduction of respiratory supporting devices/therapies. These ages will be directly obtained from the clinical reports (on report it is reported the age of the patient) of indirectly (according to the data of the report that describes the first introduction of the drug/devices or that firstly reports the loss of the ambulation)

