8.1.1 Primary endpoints

To describe the natural history of the LGMD 2E

To define of the clinical variables that more strongly relate with the evolution of the disease

To identify any possible correlation between variables

To identify any possible correlation between variables and clinical outcomes

To identify any possible correlation between phenotype and genotype

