8.2.2 Inclusion criteria

Will be included only those patients, both adults and minors, that have a genetical diagnosis of LGMD 2E and that will sign the specific informed consent for data management.

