8.2.3 Exclusion criteria

Th lacking subscription of informed consent and or the lack of genetic diagnosis represent the only exclusion criteria.

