8.3 Variables

Will be extract from the clinical charts of these patients, after the sign of the informed consent for the data management, only retrospective data (therefore all those data older than the day of the recruiting visit).

These data will be reported in a excel file specifically created. On this file data will be anonymized through a patient identification code that will be decrypted in another separate file. For this file will be considered the following data:

a) Dati anagrafici:

1. Anonymized name
2. Sex
3. Age

Form 2- DIAGNOSIS:

- 1) Age at onset
- a) clinical presentation
- b) clinical progression
- 2) CK at onset
- 3) EMG

4) Biopsy:

- a) Histology
- b) Immunohistochemistry
- c) Western Blot

5) Genetic:

- a) In frame del/dupl
- b) Out of frame del/dupl
- c) Missense
- d) Nonsense

Form 3- CLINICAL DATA AND TREATMENTS:

Hospitalization: Data – Cause – Frequency* Surgery: Data – Complications* Fractures: Data – Frequency – Location* Fell: Data – Frequency* Emergency Room Accesses: Data – Cause*

APPARATUS

Skeletal-Muscle

1) Clinical tests:

NSAA* MFM* QMT* Brook Scale* Egen Klassifikation* Barthel Index* Walton and Gardner* & Medwin GSGC* Grip Strength (quantitative)* Handheld Dynamometry* Performance of the Upper Limb Module for DMD 2.0* 10m Walk: 1- normal, 2- slightly impaired- 3 moderately impaired- 4- impaired- 5 with device - 6 not walking but stands- 7 wheelchair 6MWT* time to rise from the floor* Climb 4 stairs (1 no help - 2 one hand on the leg – 3 two hands on the legs - 4 stand with help -5 Handrail - 6 hardly climbs- 7 Not able). 10m Run

Time to rise from a chair (1 Normal - 2 with difficulties -3* helping with one hand - 4 Helping with two hands - 5 other helps - 6 Impossible). Time to stand from the floor (1 Normal - 2 first rise the pelvis and then one hand on the floor - 3 First rise the pelvis and then two hands on the floor - 4 One hand on the leg - 5 Two hands on the legs - 6 Other help - 7 Impossible).

Neuromuscular evaluation (date): maximal voluntary strength: bilateral knees extension, Isometric contraction test*, bilateral knee flexion, Workspace volume

2) Exams:

CK* Muscular RMN

3) Symptoms:

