8.5 Cohort dimension

Expected cohort dimension is of 33 patients that is the number of patients followed at the Neurological Unit in the last 10 years. Statistical analysis will be based on generalized linear regression models, suitable both for continuous variables both for independent ones. Variables with a nonlinear distribution will be used only in logarithmic scale. Only data corresponding to yearly visit (at least two data in two years) will be used for the linear correlation analysis and in multivariate correlation models. Furthermore, to verify the accuracy of clinical variables in

describing the evolution of the dystrophy, variables will be coupled and compared by a bivariate analysis.

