8.7 Data analysis

Analysis will be performed using generalized linear regression models suitable both for continuous variables both for independent ones. Variables with a nonlinear distribution will be transformed in logarithmic scale before the analysis to be performed. For any analysis data will be divided according to the age of the patient at the moment of the evaluation. Data will be analyzed with linear correlation both compared to the variable age both in bivariate models and multivariate models. Results obtained will be adjusted for confounding factors not related to muscular dystrophy.

Data of included patients will be globally studied and divided in two groups homogeneous for genotype.

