8.7.1 Primary endpoints: analysis

- To obtain a variables distribution according to patients' age and to verify possible correlations with the disease's progression.
- To study possible correlation between variables identified.
- To evaluate possible connections with clinical outcomes

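### The clinical outcomes are ages at milestones, but the stated regression approach has no place for patients who have not yet reached them

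*Protocol*

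**What the plan says.** - **Outcome.** Protocol 8.4: "Clinical outcomes will be defined as the age of loss of ambulation, the age of introduction of cardiological supporting drugs", with the age at first respiratory device or therapy as the third. Each age is taken from the report that first records the event. Nothing is said about a patient with no such report.
- **Who enters.** Protocol 8.2.2: "Will be included only those patients, both adults and minors", given a genetic diagnosis and consent. According to 8.2.3, missing consent or "the lack of genetic diagnosis represent the only exclusion criteria". No milestone has to have been reached.
- **End of observation.** Protocol 8.3 extracts "only retrospective data (therefore all those data older than the day of the recruiting visit".
- **Method.** Protocol 8.5: "Statistical analysis will be based on generalized linear regression models". Section 8.7 repeats this and adds log transformation, linear correlation, and bivariate and multivariate models. It also says: "Data of included patients will be globally studied and divided in two groups homogeneous for genotype".
- **Use of the outcomes.** A primary endpoint in 8.1.1 is "To identify any possible correlation between variables and clinical outcomes". The matching analysis in 8.7.1 is "To evaluate possible connections with clinical outcomes", with no other method named.

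**The concern.** An age at a milestone exists only once the milestone has happened. For a patient who still walks, takes no cardiac drug or needs no respiratory support at the recruiting visit, the protocol's outcome has no value. What is known is that the age exceeds the age at last information. Ordinary regression or correlation on milestone age drops that patient.

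The loss is not random. Among patients of a given current age, those with late milestones are the ones missing, so the remaining ages are too early and become tied to current age. If the two genotype groups were seen at similar ages, a true difference shrinks. If they were seen at different ages, it can be inflated, hidden or created from nothing.

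Natural history, correlation with clinical outcomes and genotype-phenotype correlation are all primary endpoints, and sections 6 and 7 intend the results to support follow-up guidelines. The trajectories of the repeated yearly measures are not affected.

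**Working it through.** **No stated figure to reproduce.** The 33 in section 8.5 is a count of patients followed at the unit over 10 years. The protocol gives no milestone ages, event rates or age distribution. The figures below are simulations under assumptions and show mechanism and range only.

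**Assumptions (not from the protocol).** Milestone age T is Weibull with shape k and median m, so scale = m / (ln 2)^(1/k). Visit age C is uniform from 5 to 45 years unless stated. The event is seen if T ≤ C. The event-only analysis uses T among those patients.

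**Step 1: one group** (k = 2.5; range for k = 1.5 to 4 in brackets).

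| True median (y) | Left out of 33 | Event-only median (y) | Correlation of T with C |
|---|---|---|---|
| 12 | about 6 | 11.1 (9.8 to 11.7) | 0.24 |
| 18 | about 11 | 15.7 (12.5 to 17.0) | 0.38 |
| 25 | about 17 | 19.5 (14.5 to 22.6) | 0.48 |

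The correlation with current age arises purely from the selection.

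**Step 2: two genotype groups of 17 and 16** (k = 2.5). The mean is scale × Γ(1 + 1/k). With (ln 2)^0.4 = 0.864 and Γ(1.4) = 0.887, medians of 12 and 18 years give means of 12.3 and 18.5, a true difference of 6.2 years.

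| Visit ages, earlier vs later group (y) | Event-only difference (y) | Same, adjusted for current age (y) | Rejected: event-only pooled t | Rejected: log-rank, all 33 |
|---|---|---|---|---|
| 5–45 vs 5–45 | 4.7 | 4.3 | 44% | 65% |
| 5–25 vs 15–45 | 6.4 | 2.7 | 71% (inflated by visit age) | 59% |
| 15–45 vs 5–25 | 0.3 | 1.5 | 5% | 58% |

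Same-shape Weibull groups have proportional hazards, which favours the log-rank test.

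**Step 3: no true difference** (both medians 18 years).

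| Visit ages (y) | Spurious event-only difference (y) | False positives, pooled t |
|---|---|---|
| 5–40 vs 10–45 | 0.65 | about 5% |
| 5–35 vs 10–45 | 1.45 | 7% |
| 5–25 vs 15–45 | 4.4 | 23% (Welch 30%) |

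In the last setting the log-rank test rejects in 5%. Adding current age as a covariate cuts the spurious difference to 0.8 years and false positives to 3%.

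**Step 4: does keeping event-free patients repair it?** In samples of 33 without deaths and visit ages 5–45, the mean Kaplan-Meier median is 18.1 years (true 18) and 25.3 years (true 25). A separate simulation with shape 3, visit ages up to 35 or 50 and medians of 12 to 35 years showed the same direction throughout. Its log-rank power exceeded event-only power in every setting, for example 0.64–0.75 against 0.23–0.48 for medians of 16 vs 24 years.

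**Step 5: limit of the repair.** Suppose only living patients are recruited, death follows the milestone after a gamma-distributed gap (shape 4), and the true median is 18 years.

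| Mean gap to death (y) | Kaplan-Meier median (y) | Event-only median (y) |
|---|---|---|
| 10 | 22.4 | 17.8 |
| 20 | 20.0 | 17.0 |
| 30 | 19.1 | 16.5 |

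Censoring restores the event-free patients but does not correct survivor selection.

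**The case against.** **The exclusion is inferred, and details may sit in an SAP.** The protocol never says that event-free patients are dropped. Generalized linear models can keep them, for instance by modelling milestone status by age, and section 8.3 collects the inputs. This is fair as far as it goes. But no such model is described, and the defined outcome is the age itself. The protocol states both the form of the outcome and the model family, and as described they do not fit.

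**Section 8.7 divides data by age at evaluation and adjusts for confounding.** If current age is adjusted for, most of the spurious difference goes. However, the true 6.2 years then reads 4.3, 2.7 or 1.5 years, so adjustment exchanges one error for another.

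**The size is uncertain.** This stands. The large spurious difference needs strongly unequal visit ages, and milder imbalance gives little. For an early milestone (true median 12 years) the bias is about 1 year at shape 2.5. Section 6 describes early onset, but it also places respiratory and cardiac involvement in the last stages. Two of the three outcomes concern those systems, where more patients are likely to be event-free.

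**The remedy is not closer in every scenario.** Under survivor selection the event-only median was nearer the truth for gaps of 10 and 20 years. That is two errors offsetting by chance, which no analysis should rely on. It is a reason to state the limitation. Self-referral applies only to the patient-association route in section 8.2.1, not to the unit's own patients.

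**The study is exploratory.** True, and section 8.9 warns of too few data. It does not mention event-free patients, and the outcomes affected are primary.

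**Conclusion.** The concern holds. Sections 8.2.2, 8.2.3, 8.3 and 8.4 together create outcomes with no value for event-free patients, and sections 8.5, 8.7 and 8.7.1 describe no method that keeps them. The direction of this particular error, milestone ages too early, does not depend on the assumed values. Its size does: from about 1 year for a median of 12 to about 5.5 years for a median of 25 at shape 2.5 and visit ages 5–45, with the genotype contrast movable either way. The net error is not fixed by the protocol, because survivor selection may pull in the opposite direction. This should be fixed before analysis; the data remain usable.

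**What to change.** **In 8.4 and 8.7:**
- For each milestone, derive event status from data already collected under 8.3 (walking grade, loss of ambulation, wheelchair, respiratory support, dated therapies), and add the age at last chart information.
- Analyse the three outcomes as time-to-event on the age scale, censoring event-free patients at that age.
- Report the number of events and Kaplan-Meier median ages with 95% confidence intervals, or the proportion event-free at fixed ages where the median is not reached.
- Relate genotype and clinical variables to the outcomes by Cox regression (Firth-penalised if events are few) or parametric survival regression, with few covariates given 33 patients.
- Keep generalized linear models and linear correlation for the repeated yearly measures.

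**In 8.9:** state that recruiting living patients, some of them self-referred through the association, may select survivors, and that this analysis does not correct for it.

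**Optional:** in a sensitivity analysis, treat loss of ambulation dated only by its first report as interval-censored.

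**Cost:** wording in three sections, one added column from the same charts, standard software and no extra patients. Intervals will be wider, and a late median may not be estimable. At n = 33 and shape 2.5, that happens in about 20% of samples for a true median of 35 years with visit ages 5–45. With visit ages 5–30 it happens in 29% of samples for a true 25 years and 81% for a true 35 years.

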Guidelines will uniform the clinical approach to this disease, both on the National and the international scenario, and will improve the use of sanitary resources. Furthermore, with a phenotype-genotype correlation study, it will be possible to recognize those patients that are more at risk to develop a more severe disease.

7. Research query and objective

The lack of data on natural history of this rare disease and the need to define guidelines for the best follow up of these patients, compelled us to set up this study. In this study any investigation performed in patients affected by LGMD 2E will be considered with the aim to recognize the progression of the disease and those variables that are more useful and precise in describing its evolution. Primary objective of the study is to obtain more and better knowledge of this rare group of LGMD, describing its natural history through the analysis of clinical charts of the more affected patients possible.

To select clinical variables that are more useful to define the evolution of the disease and to identify any possible differences in clinical presentation that might be due to differences in genotype-phenotype correlation. Secondary objective of the study is to demonstrate the real impact of cardiopulmonary impairment on the prognosis of these patients.

Thank to these knowledges, to lead to a better therapeutic approach to this disease, stimulating the development of new drugs.

8. Methods

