8.1.2 Secondary endpoints

To define the better follow up routine for LGMD 2E patients in view of possible genetic differences

To define those therapies that are able to slow the progression of the disease

To ameliorate the use of sanitary resources for the management of these chronic patients.

To gain new knowledges that could be used for the development and the management of future new therapies.

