Loss of independent ambulation* Calf hypertrophy (Unilateral/Bilateral, if bilateral → Symmetrical/Asymmetrical)* Calf atrophy: Unilateral/Bilateral, if bilateral → Symmetrical/Asymmetrical)* Tendon contractures* Scoliosis Scapular winging* Tiptoe gait pattern* Muscle pain* Muscular trophism* Muscular weakness (Symmetrical/Asymmetrical - Proximal/Distal - Progression: chronic/acute)* Muscle contractures (Unilateral/Bilateral - site*

Cramps: Severity – Frequency)* Clubfoot (Unilateral/Bilateral)* Spine anomalies* Ability to walk on toes* Fasciculations* Percussion induced muscular contractions* Macroglossia (yes/no)* Dysphagia(yes/no, Data onset, Progression chronic/acute, Severity-> light/moderate/severe, frequent aspirations:yes/no)

4) Muscles involved: shoulder* arms* forearms* hand* spine* pelvic muscles* thigh* leg* feet

5) Wheelchair: yes/no; if yes → changed through the years – still using yes/no – how long*-other ambulatory devices yes/no; if yes → name → still using yes/no – how long – has it been changed through the years?

6) Deambulation and motility: general comments* Electromyography*

Cardiovascular

1) Evaluations (data): general conditions: using devices to support heart function (eg. pacemakers, ICD, etc.) - name* still using? – How long? - has it been changed through the years?

2) Conduction system anomalies:

EKG * Holter EKG* Echocardiogram* events monitoring*

3)Cardiomyopathy* Heart RM*

4) Symptoms: basal rattling* Oedemas* slopes edemas * Holter* Echocardiogram: Description* FE* Left ventricle telediastolic Volume* Left ventricle telediastolic diameter* Ahythmies* Coronaropathy* Valve* Pulmonary hypertension* Palpitations* Syncope* almost syncope*

Respiratory

1) Evaluations (data):

2) Respiratory support: Invasive/ Noninvasive* Cough assist* Cough peak* Overnight BiPAP * Other*

3) Respiratory status* Pulsoxymetry/polysomnography (mean SpO2 - SpO2 minimal - FC mean - AHI – ODI – %* MVV – MIP – MEP. Dispnoea: supine position– stress induced – at rest*

4) Quality of sleep: daily somnolence* not restorative sleep* frequent overnight awakening* morning headaches* daily fatigue*

Laboratory Tests

1)Imaging tests (data): RX thorax* RX spine* RM muscle*

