2) Blood tests: Glucose* Proteins* Hemoglobin* White blood cells* Neutrophils *INR* RATIO* CPK* LDH* Amilase* Cistatine C* AST * ALT * ALP * GGT * Bilirubin total/direct/ indirect* Creatinine* Electrolytes (Sodium – Potassium - Clorum – Calcium total/ionized)* Urine (macroscopic view - blood (Yes/No) – anomalies)*

3) Bone status: MOC - PTH pg/mL - VIT D1,25 pmol/L-VIT D 25 nmol/L*

4)Glycemic state: Insuline - Hb1aC* Pro BNP*

Autoimmune disease

Name*

Treatment*

Therapy

1) Name - posology – data – rationale

2) Prescriptions*

3) Pain therapy*

4) Steroids*

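### The cardiac outcome in Section 8.4 counts drugs but not devices, so patients with device-only or undrugged cardiac disease have no cardiac outcome age

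*Protocol*

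**What the plan says.** Section 8.4 fixes three clinical outcomes, all of them ages. The first is loss of ambulation. The other two are "the age of introduction of cardiological supporting drugs and the age of introduction of respiratory supporting devices/therapies". Where the age is not stated directly, it is found "according to the data of the report that describes the first introduction of the drug/devices". No diagnosis, ejection fraction or indication is required for the cardiac age to be set.

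The Section 8.3 form collects much more on the heart. It has an entry for "using devices to support heart function (eg. pacemakers, ICD, etc", one for "3)Cardiomyopathy* Heart RM", and further entries for conduction anomalies, ejection fraction, left ventricular volume and diameter, and arrhythmias. Under Therapy it records "Name - posology – data – rationale" for each treatment.

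Three stated aims bear on this outcome:
- a primary endpoint in 8.1.1: "To identify any possible correlation between variables and clinical outcomes";
- the secondary objective in Section 7: to "demonstrate the real impact of cardiopulmonary impairment on the prognosis of these patients";
- a secondary endpoint in 8.1.2: "To define those therapies that are able to slow the progression of the disease".

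**The concern.** The two support outcomes sit in one sentence but follow different rules. Starting a respiratory device sets the respiratory age, while receiving a cardiac device does not set the cardiac age. The cardiac age is also tied to a prescribing act and not to a cardiac finding. It can be absent in a patient whose chart documents heart disease, and present in a patient whose chart documents none.

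This matters because the outcome enters a primary endpoint. Patients without a cardiac age cannot contribute to correlations that use it, and those lost would be selected by how their heart disease was managed. In a cohort of 33 that is also divided into two genotype groups (Section 8.7), losing a few patients with real cardiac disease could change what is seen.

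**Working it through.** No power or sample-size figure bears on this point, and 33 is a clinic count, not a calculated number. The check sets the definition in 8.4 against the items in 8.3.

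**Applying the definition case by case**

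| Patient, as documented in the charts | Collected in 8.3? | Cardiac outcome age under 8.4? |
|---|---|---|
| Cardiac drug started for documented impairment | Yes | Yes |
| Pacemaker or ICD, no cardiac drug | Yes | No |
| Cardiomyopathy or reduced ejection fraction, no drug or device | Yes | No |
| Cardiac drug started, no impairment documented | Yes | Yes |
| No impairment, drug or device | Yes | No |

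Rows 2 and 3 give the same result as row 5, and row 4 gives the same result as row 1. On this outcome the definition does not separate diseased patients without a drug from unaffected patients.

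A patient in row 2 who later receives a drug is dated at the drug, not at the device.

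**Illustration of scale**

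Inputs from the Protocol:
- expected cohort 33 (Section 8.5);
- more than 60% of patients with heart failure (Section 6, a cited background figure).

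Assumptions, since the documents give no figure:
- 60% applies to this cohort;
- a share *p* of those with heart failure never had a cardiac drug, with *p* from 10 to 30%.

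Patients with heart failure: 0.60 × 33 = 19.8, about 20.

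Patients with heart failure but no cardiac outcome age: 19.8 × *p*.

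Apparent cardiac proportion: 60% × (1 − *p*).

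| *p* (assumed) | Without a cardiac outcome age | Apparent cardiac proportion |
|---|---|---|
| 10% | 1.98, about 2 | 54% |
| 20% | 3.96, about 4 | 48% |
| 30% | 5.94, about 6 | 42% |

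Row 4 cannot be sized from the documents. A drug started before any impairment would put the apparent age of cardiac involvement too early, by an unknown amount.

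**The case against.** **The later mention of drugs and devices together in 8.4 may cover cardiac devices.** That phrase says how dates are found, and the respiratory devices just named explain it. It does not extend the cardiac definition. If the sponsor meant it to, the definition still needs rewording.

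**The cardiac data are not lost.** This stands. Cardiomyopathy, ejection fraction and the rest are collected, and 8.7 plans to analyse variables against age and against each other. The natural history of the heart can be described whatever 8.4 says. The Section 7 objective treats impairment as a predictor of prognosis, and the 8.3 items can supply it. The fault is confined to analyses that use the cardiac outcome age.

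**A dated treatment milestone suits a retrospective chart study.** This also stands. Age at first documented involvement depends on when and where patients were examined, so a straight replacement would exchange prescribing variation for surveillance variation. It would also build the outcome from variables that the primary endpoint correlates with it. That argues for adding the involvement age beside the support milestone.

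**Drugs may be given only to support impaired function.** The wording allows that reading, and the rationale for each therapy is recorded. The definition does not use that rationale, however, so nothing enforces the reading.

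**The therapy analysis is already disclaimed.** Section 8.9 concedes that the study will not give reliable information on the impact of therapies on progression. It puts this down to the lack of natural history data and does not address the outcome definition. The primary correlations are unaffected by that concession.

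**Conclusion.** The point holds in a limited form. Section 8.4 leaves cardiac devices and undrugged cardiac disease without an outcome age, treats the heart differently from the lungs in the same sentence, and lets a drug start count without documented impairment. The number of patients affected is unknown. The 2 to 6 of 33 above rests wholly on the assumed 10 to 30% and on applying the 60% background figure to this cohort.

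A reader might infer more than the documents support:
- *That such patients count as event-free.* The protocol sets no event or censoring rule and plans generalized linear regression and linear correlation. The age is simply missing.
- *That about 20 patients are misclassified.* Twenty is the expected number with heart failure, and those given a drug do receive an outcome age. Patients treated before impairment may lie outside the 20.
- *That outcome ages are wrong by a stated number of years.* The documents give nothing on the gap between cardiac involvement and first drug.
- *That a cardiac drug is planned as both outcome and exposure.* Section 8.1.2 names no cardiac drug, and no planned analysis sets cardiac drugs against age at drug start. Nothing excludes it either, so a one-line safeguard is worth having.

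The change should be made: an outcome used in a primary endpoint is affected, and the correction is cheap.

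**What to change.** Amend Section 8.4 as follows.

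1. Define the cardiac support outcome as age at first cardiac supporting drug or device, whichever comes first, to match the respiratory wording.
2. Report beside it, as a separate outcome, age at the first chart documenting cardiac involvement: cardiomyopathy, reduced ejection fraction as reported, or arrhythmia or conduction disease. State that this age will not be correlated with its own component variables.
3. State that age at cardiac drug start will not serve as a progression outcome in any analysis of cardiac therapies.

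The cost is protocol wording, one redefined variable and one added derived variable, all from items already in 8.3. The downside is that the involvement age is less certain where early cardiac tests are missing, so it supplements the support milestone and does not replace it. The change concerns outcome definitions only and implies nothing about how patients should be treated.
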